Surveys will be conducted at approximately 6 weeks (baseline), 6 months, and 12 months after injury. We anticipate that roughly 3,120 workers in WA and 525 workers in OH will complete baseline surveys. Based on estimated response rates, we anticipate roughly 1,700 completed 12-month outcome surveys from WA and 234 from OH. Depending on survey eligibility and response rates, up to 100% of survey

respondents may be drawn from the underlying WA/OH cohorts (however, it is possible that survey accrual may need to continue beyond cohort accrual).

The primary predictor is binary (1 for WA cases, 0 for OH cases). We will specify GEE panel models as described for Analysis Topic B to account for outcome measures at multiple time points for each patient (6 months, 12 months). Appropriate GEE link functions will be specified for each outcome variable, e.g., identity link for continuous variables, logit link for binary variables, and log link for counts (Tables 2 and 3). Comparisons of clinically important improvements in patient pain and functioning will be based on the proportion of patients who achieve clinically meaningful improvement (relative to baseline) on our outcome measures at 6 and 12 months, as defined by 30% or greater improvement. We will include time/state interactions in order to assess (1) change in outcomes over time and (2) differences in such changes by state.

Covariates described under Analysis Topic B will also be included for this analysis, in addition to baseline covariates collected during the survey. Additional survey-based covariates will include the following (this list may be adjusted as the survey is finalized with stakeholder input):

- Education
- Household Income
- Race/ethnicity
- Health status
- Comorbidities (survey-based FCI, current cancer treatment)
- Pain intensity
- Physical function/pain interference
- Emotional functioning-Anxiety
- Emotional functioning-Mood
- Quality of life
- Work status and barriers to work
- Treatment for pain
- Satisfaction with treatment
- Communication with health care provider
- Alcohol and tobacco use

Using these covariates, we will calculate a propensity score. In order to minimize the loss of survey data, we plan to include this propensity score in the causal models along with important covariates. However, if needed to achieve balance on baseline variables, we will restrict the analytic sample to the region of common support and/or implement propensity score matching.

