We expect relatively high survey response rates, based on previous research in these injured worker populations. Barriers to recruitment include being unable to locate and contact injured workers, and injured workers choosing to not participate. The address and phone numbers of injured workers who are receiving WC benefits are largely complete and accurate because contact information is required in order to receive disability benefits. In order to increase the response rate, all eligible workers identified by WA and OH WC systems will be sent an introductory letter 1 week prior to the initiation of the phone surveys. Workers will be able to schedule a time for the survey or can opt out at that point. Workers will be paid \$50 for the baseline survey, \$30 for the 6 month survey, and \$50 for the 12 month survey (\$130 total). The University of Washington (UW) Survey Research Division (SRD) will make 10 call attempts. The SRD research staff are extensively trained in standardized interviewing techniques and methods, effective calling strategies, building rapport and interest, and refusal prevention, which all aid in minimizing attrition and maximizing response rates. The survey interviewers are trained to minimize item non-response, while supporting autonomy not to answer individual questions.

Based on these efforts, we anticipate limited amounts of missing data for individual survey items, under 5%. We do expect larger and non-negligible amounts of missing 12-month outcome data relative to 6-month outcome data on the surveys, based on projected attrition.

We will use standard techniques to identify the nature (randomness) of missing data. Where missing data are minimal (<5%) and random (no clear associations with outcomes or predictors of interest), we will use casewise deletion; we expect this approach will be adequate for administrative data and baseline survey data. For the GEE panel models testing survey-based patient outcomes, we will use multiple imputation methods, based on an expected larger amount of missing data and the likely association of missingness with previous unsafe opioid prescribing.⁴

⁴ Aloisio, K. M., Swanson, S. A., Micali, N., Field, A., & Horton, N. J. (2014). Analysis of partially observed clustered data using generalized estimating equations and multiple imputation. *Stata J*, 14(4), 863-883.

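### In Topic C and the matching Topic I sensitivity analysis, casewise deletion over 15 baseline survey covariates can lose far more than the 5% expected for any one item

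*Combined protocol and SAP*

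**What the plan says.** All references are to Section 7 of the combined protocol and SAP.

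- **Expected item non-response (Missing Data).** "we anticipate limited amounts of missing data for individual survey items, under 5" percent. This is a ceiling. No rate is given for any item.
- **Deletion rule (Missing Data).** "Where missing data are minimal (<5%) and random (no clear associations with outcomes or predictors of interest), we will use casewise deletion". The unit of the 5% (item, scale or model) is not stated. The sentence runs on to say where deletion should suffice: "we will use casewise deletion; we expect this approach will be adequate for administrative data and baseline survey data".
- **Imputation (Missing Data).** "For the GEE panel models testing survey-based patient outcomes, we will use multiple imputation methods". The reasons given are a larger expected amount of missing data and a likely link between missingness and earlier unsafe prescribing.
- **Covariates (Topic H).** "Covariates described under Analysis Topic B will also be included for this analysis, in addition to baseline covariates collected during the survey". Fifteen survey covariates are then listed, from education to alcohol and tobacco use, and the list may be adjusted. The propensity score is calculated from these covariates.
- **Where they meet an administrative outcome.** Topic C repeats the Topic B test of Hypothesis 1 in survey respondents, adding the baseline survey covariates and the Topic H propensity score methods. Topic I includes the same sensitivity analysis for COHE against non-COHE within Washington.

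**The concern.** A low rate on each item does not mean a low rate of incomplete records. Under casewise deletion, a worker missing any one of the 15 covariates has no propensity score and leaves the model. The share that matters is the share of workers with at least one gap, and the plan gives no figure or limit for it.

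Topics C and I are exposed because unsafe prescribing is measured from billing data. The imputation sentence is tied to survey-based outcomes, and the sentence before it assigns baseline survey data to deletion.

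Topic C exists to show whether the Topic B result survives better confounder control. If many respondents drop out for item non-response, a difference between B and C could reflect the added covariates or the reduced sample, and the two could not be separated. Ohio is the limiting group, with 525 expected baseline respondents against 3,120 in Washington.

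**Working it through.** The plan states no complete-case fraction, so there is no figure of its own to reproduce.

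**Inputs from the documents.** k = 15 survey covariates, counted from the Topic H list. Baseline respondents: 3,120 in Washington and 525 in Ohio. Both are upper limits for Topic C, which takes only respondents who belong to the cohorts. Item missingness m is under 5%.

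**Assumptions.** The same m applies to every covariate. Values of 1%, 3% and 5% are shown because no rate is given. Administrative covariates are taken as complete.

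**Independent missingness.** Share lost = 1 − (1 − m)^15.

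- m = 1%: 1 − 0.99^15 = 0.140
- m = 3%: 1 − 0.97^15 = 0.367
- m = 5%: 1 − 0.95^15 = 0.537

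**Clustered missingness.** People who skip one question tend to skip others. An equicorrelated Gaussian-threshold simulation (400,000 draws, 15 covariates) with latent correlation 0.5 gives losses of 0.088, 0.207 and 0.299.

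The last column is 1/√(1 − loss), the factor by which standard errors grow if the loss is equal in both groups.

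| m | Dependence | Lost | Ohio left of 525 | Washington left of 3,120 | SE factor |
|---|---|---|---|---|---|
| 1% | independent | 14.0% | 452 | 2,683 | 1.08 |
| 3% | independent | 36.7% | 332 | 1,976 | 1.26 |
| 5% | independent | 53.7% | 243 | 1,445 | 1.47 |
| 1% | correlation 0.5 | 8.8% | 479 | 2,845 | 1.05 |
| 3% | correlation 0.5 | 20.7% | 416 | 2,474 | 1.12 |
| 5% | correlation 0.5 | 29.9% | 368 | 2,187 | 1.19 |

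**How far the range extends.**

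- Lower rates: m = 0.5%, independent, loses 7.2%.
- Stronger clustering: correlation 0.9 loses 3.2% at m = 1%, 8.4% at 3% and 12.7% at 5%.
- Limits at m = 5%: 5% if the same workers miss everything, and 15 × 5% = 75% if no worker misses more than one covariate.
- More variables: several bullets are compound or multi-item scales. With 24 independent variables the loss is 21% at m = 1% and 52% at m = 3%.

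**What a joint limit requires.** To keep the total loss under 5% with 15 independent covariates, average missingness must stay below 1 − 0.95^(1/15) = 0.34%.

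**The case against.** Several points on the other side stand.

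- **Topics H and J.** A reader might infer that all the survey models lose respondents this way. The documents do not show that. The imputation sentence is attached to the models of survey-based outcomes, and those models contain the covariates. Whether the baseline covariates are imputed is unstated, which is an ambiguity and not a planned loss.
- **Bias.** A reader might infer that the plan would delete workers who are plainly not a random subset. The rule forbids that where an association with outcomes or predictors is clear. What remains is lost precision, plus associations too weak to detect.
- **Internal contradiction.** The Topic H statement "In order to minimize the loss of survey data, we plan to include this propensity score in the causal models along with important covariates" might look inconsistent with deletion. Its next sentence offers common support and matching as the fallback, so it concerns those choices and not item non-response.
- **Assumed rates.** The plan gives only a ceiling. Interviews are paid, and interviewers are trained to limit item non-response. Low or strongly clustered missingness gives losses of a few percent.
- **Tentativeness.** The plan will assess its missing-data assumptions on preliminary data and run sensitivity analyses if indicated.
- **Administrative data.** Washington claims and pharmacy data are described as almost fully complete, with similar completeness expected in Ohio, so they need not add to the loss.

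These points narrow the issue without removing it. Topics C and I stay outside the imputation sentence, and no joint threshold is set that would trigger reassessment. The per-item reading of the 5% rule is an inference, but it is the natural one because the only supporting survey figure is per item. Even at correlation 0.7, the loss is 15% at 3% per covariate and 22% at 5%.

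**Conclusion.** The point holds for Topic C and the corresponding sensitivity analysis in Topic I. An expectation of under 5% missing per item does not support casewise deletion over 15 covariates used jointly. For item rates of 1% to 5%, the loss is 14% to 54% under independence and about 9% to 30% with latent correlation 0.5. In Ohio that leaves about 479 down to 243 of 525. These figures rest on assumed rates, a common rate across covariates, and a list that may still change.

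The issue is moderate. Topic C is a sensitivity analysis. A reader might infer that the primary test of Hypothesis 1 is weakened, but Topic B uses the full administrative cohorts and no survey covariates, so it is untouched. For Topics H and J the plan needs only a clarifying statement.

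**What to change.** In the Missing Data text:

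1. Define the 5% limit as the share of workers missing any covariate in the model or propensity score, and keep the randomness condition.
2. Multiply impute the baseline survey covariates in Topic C and the Topic I sensitivity analysis. Include the prescribing outcome and the exposure (state or COHE status) in the imputation model, compute the propensity score within each imputed data set, and pool the estimates.
3. State that the imputation already planned for Topics H and J includes the baseline covariates and the propensity score.
4. Report the complete-case fraction by state and by COHE status, with the complete-case result alongside.

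With imputation, no respondent would be lost to item non-response on these covariates. The cost is SAP wording and a larger imputation model. No new data are needed.

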1	F. Subgroup response to opioid review decisions	Subgroup analysis using PDMP data	Opioids obtained from different prescriber or different payer	OH/WA cohorts
1	G. Describe usual care	Descriptives (rates)	Health care utilization	OH/WA cohorts
2	H. PA vs RR	GEE/propensity score & subgroup analysis	Secondary outcomes	OH/WA survey samples
2A	I. COHE vs non-COHE	GEE/propensity score & subgroup analysis	Unsafe opioid prescribing	WA cohort & survey sample
2A	J. COHE vs non-COHE	GEE/propensity score & subgroup analysis	Secondary outcomes	WA survey sample

Admin, administrative data; COHE, Centers of Occupational Health and Education; GEE, generalized estimating equations; ITSA, interrupted time series analysis; OH, Ohio; PA, prior authorization; RR, retrospective review; WA, Washington.

Aim 1

Specific aim 1. Examine the comparative effectiveness of prospective prior authorization (PA) with hard stops in WA versus retrospective review (RR) with prescriber notification in OH in reducing unsafe opioid prescribing.

Hypothesis 1. Prospective PA with hard stops (WA) will be associated with statistically significantly less unsafe opioid prescribing compared to RR and prescriber notification (OH). [See Analysis Topic B]

Aim 1. Analysis Topic A: Compare long-term prescribing patterns across states and identify discontinuities

This analysis will be based on a time series approach. We will construct data points for each month from January 1, 2010 through December 31, 2020. For each state, we will construct two separate time series. The first is the proportion of WC claims with any opioid prescription in the acute phase (0-6 weeks). The second is the proportion of WC claims with unsafe opioid prescribing (defined earlier) during the subacute phase (6-12 weeks). For each, calendar month denominators for the time series will be assigned based on date of injury, and numerators will be calculated for each one-month set of claims using the pharmacy billing data for up to three months after date of injury.

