The resulting four time series will be inspected to identify secular trends and discontinuities/unexpected changes that might indicate a policy or regulatory action, or an external factor that might have affected opioid prescribing pattern. A timeline of opioid-related policy events affecting WA and/or OH (e.g., legislation, regulations, guidelines, large-scale interventions) will be constructed and overlaid on these time series to assess patterns and potential confounding related to the state-based environments. As part of Aim 3 (described below), qualitative methods will be used to understand the causes of unexplained fluctuations.

Finally, we will test whether implementation of the WA PA program (implemented in July 2013) or the OH RR program (implemented in March 2019) was associated with a statistically significant reduction in the rate of unsafe opioid prescribing using standard interrupted time series analysis (ITSA) techniques.^{1,2}

Aim 1. Analysis Topic B: Compare PA to RR with respect to unsafe opioid prescribing

This analysis is focused on the primary outcome for this study, unsafe opioid prescribing (defined earlier), using administrative data for the full WA and OH cohorts. We are planning for a one-year prospective timeframe, beginning July 2019 (based on dates of injury). Our cohort size estimates are 4,636 eligible workers in WA and 779 in OH .

Using WC claims and billing data from each state, we will track opioid prescribing for each injured worker for a full year after date of injury in order to test Hypothesis 1: Prospective PA with hard stops (WA) will be associated with statistically significantly less unsafe opioid prescribing compared to RR and prescriber notification (OH).

The primary outcome is the composite unsafe prescribing measure (i.e., meeting one or more of the 3 chronic-phase criteria in Table 1), modeled longitudinally over the three 3-month time windows, in order to assess the comparative effectiveness of PA/RR on the transition from early opioid therapy to longer-term unsafe opioid prescribing. Generalized estimating equations (GEE) panel models will be used to account for outcomes being measured during several time windows within individual patients.³

¹ Linden, A. (2015). Conducting interrupted time series analysis for single and multiple group comparisons. *The Stata Journal*, 15(2), 480-500.

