During Year 2, we will conduct key informant interviews with policy makers and stakeholders who were involved in the creation and implementation of each state's ORP, including ORP reviewing pharmacists and nurses. Initial key informants in each state have already been identified; these are individuals, as available, who were important in the ORP design and implementation process (however, we will be unable to interview current and former BWC employees due to an ongoing lawsuit in OH). The remainder of the key informants will be identified through (a) snowball sampling, by asking each interviewed informant to name others involved in the policy-making process in their state, and (b) noting the identity of key players in ORP design and implementation mentioned in the policy documents we collect and explore. Each interview is likely to last 60-90 minutes. Key informants will be asked to share a range of information about the policy making process, including the origins of the ORP regulations about which they have expertise; considerations & alternatives explored; inputs to the policy-making process; how the specifics were designed and implemented; how necessary resources were obtained; push-back, setbacks, and decision-making milestones. Interviews will be digitally recorded and professionally transcribed. Once an initial picture of the policy development process has been obtained through key informants, policy documents that could provide additional details will be collected and analyzed. These documents may include reports, transcripts, testimony, position statements, policy drafts, and other materials produced by policy makers, issue stakeholders, executive agencies, and legislative hearings and committees.

Key informant interviews and policy document collection will be designed initially around Aim 3, but expanded to generate the data necessary to address Aim 1 as well. We will employ qualitative methods to understand the causes of unexplained fluctuations in the time series described in Analysis Topic A. Specifically, we will conduct targeted key informant interviews and analyze the specific policy documents most relevant to the time period immediately prior to any observed fluctuations. Interviews and document analyses necessary to complete Aim 1 will be timed to occur in tandem with the larger set of key informant interviews and policy documents necessary for Aim 3.

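### The search for causes looks back from a plotted change, but on the injury-month axis a prompt cause of a change in subacute prescribing can fall up to about three months after it

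*Combined protocol and SAP*

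**What the plan says.** Section 7, Aim 1, Analysis Topic A, builds two monthly series per state: any opioid prescription at 0-6 weeks, and unsafe prescribing at 6-12 weeks. On the time axis it says that "calendar month denominators for the time series will be assigned based on date of injury", and that "numerators will be calculated for each one-month set of claims using the pharmacy billing data for up to three months after date of injury". A fill made up to three months after injury is thus credited back to the month of injury.

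Two steps then look for causes. In Topic A, a timeline of policy events "will be constructed and overlaid on these time series to assess patterns and potential confounding related to the state-based environments". In Section 8, under Key Informants, the plan states: "We will employ qualitative methods to understand the causes of unexplained fluctuations in the time series described in Analysis Topic A". It then directs targeted interviews, and an instruction to "analyze the specific policy documents most relevant to the time period immediately prior to any observed fluctuations".

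Nothing in the plan shifts the timeline, re-indexes the series by fill date, or carries the search past the injury month at which a change is seen.

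**The concern.** The axis records when workers were hurt. The subacute outcome records what was prescribed one and a half to three months later. If a payer rule or law changes prescribing from a given date, workers already injured but still approaching or inside their 6-12 week window are affected, so the plotted series moves at injury months that precede the rule. A search confined to the time just before the plotted change then points away from the cause.

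The overlay shares the offset: read at face value, the real event sits to the right of the change that it produced and looks like a consequence or a coincidence. A change left unmatched there counts as unexplained and passes to the backward-looking search.

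These steps are meant to reveal state-level confounding. With one state per program, a misdated or misattributed event could distort how the Washington-Ohio contrast is interpreted. Targeting of documents matters more in Ohio, where Section 8 says that current and former employees of the state agency cannot be interviewed.

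**Working it through.** The plan gives no figure to reproduce here; the check is date arithmetic.

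**Inputs.** From Topic A: points indexed by injury month, acute window 0-6 weeks (days 0-41 after injury), subacute window 6-12 weeks (days 42-83). The two dated events in Topic A, July 2013 (WA) and March 2019 (OH), serve only as example dates. The plan gives months, so the day is assumed.

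**Assumptions.** The event acts at once on fills dated T or later; injuries and fills are spread evenly over days.

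**Formula.** For injury day i, the number of subacute days on or after T is min(42, max(0, i + 84 - T)). Sum over the days of the injury month and divide by 42 × days in the month.

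**Subacute series, T = 1 July 2013.**
- March: the last injury day plus 83 days is still before T, so 0%.
- April: injuries on 9-30 April contribute 1, 2, ..., 22 days, sum 253. 253 / (30 × 42) = 253/1260 = 20%.
- May: 1-20 May contribute 23 to 42 days, sum 650; 21-31 May contribute 11 × 42 = 462. 1112 / (31 × 42) = 1112/1302 = 85%.
- June: 100%.

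**Other event days, subacute series.** For T = 1 March 2019: December 23%, January 88%, February 100%. For T = 31 March 2019: January 25%, February 88%, March 100%. In every case the change starts before the event's own month. That month is always at 100%, because the earliest subacute day for any injury month falls on the 12th of the next month or later.

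**Acute series, T = 1 July 2013.** The same method over days 0-41 gives May 5%, June 63%, July 100%. The lead is at most about 6 weeks.

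**Sensitivity to where fills fall in the window (T = 1 July 2013).**
- All in the first two weeks (days 42-55): April 0%; May (105 + 11 × 14) / (31 × 14) = 259/434 = 60%; June 100%.
- All in the last two weeks (days 70-83): April (105 + 8 × 14) / (30 × 14) = 217/420 = 52%; May 100%.

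**Sensitivity to delay in effect (event on 1 July 2013).**
- 61 days: June 20%, July 85%.
- 84 days: June 0%; July 465/1302 = 36%; August (438 + 798)/1302 = 95%.

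At 84 days no part of the change precedes the event month, and looking backward is then correct.

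**How far forward a search must reach.** The last injury day of month m plus 83 days always falls in month m+3; plus 41 days, always in month m+2.

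**The case against.** The strongest reply is that the lead depends on how the cause acts. A cause that applies by injury date, works through earlier acute prescribing, or takes about 12 weeks to bite falls at or before the plotted change. The documents give no uptake times, and delay is plausible: Section 5 puts Ohio's review at 12 weeks, so it cannot act directly on the reviewed worker's own 6-12 week window. This stands. A reader might infer that the true cause always falls after the change and is always missed, or that slower uptake only blurs the picture; the 84-day result refutes both.

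Second, the search in Section 8 is not the plan's only tool. The Topic A overlay is not limited to events before a change, the wider Aim 3 interviews and documents continue, and policy drafts, testimony and hearings can predate an effective date. This also stands: a later cause is not excluded by rule and may surface anyway. It softens the problem without removing it, because the overlay has no lag and the targeted search has a stated direction.

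Third, the Section 8 wording might mean the time before the change in prescribing rather than before the plotted point. It names no axis, and the only axis that the plan defines for these series is injury month.

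Fourth, the percentages are shares of days, not of effect. That is right: the subacute outcome is a threshold of more than 7 days' supply, so partial shares measure exposure only. Months at 100% do not depend on how fills are spread.

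**Conclusion.** The concern holds conditionally. For a cause that acts promptly on fills by calendar date, the plotted subacute change begins up to about 3 months before the event, and the acute change up to about 6 weeks before. The stated search direction and the unlagged overlay may then miss the cause or credit an unrelated earlier event. The size rests on prompt action and even spread. Moving the fills within the window changes the May share from 85% to between 60% and 100%, but a delay of roughly 12 weeks or more removes the lead.

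A reader might also infer that the interrupted time series tests of the two programs are misdated, or that the primary result is at risk. The documents do not support either. Topic A names the implementation months without saying how they will be coded on the injury-month axis, and Topic B follows individual workers for a year from injury and does not use these series. The point is confined to the explanatory search and the overlay. It is worth correcting because it concerns a stated rule and the correction is nearly free.

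**What to change.** In Section 8, Key Informants, state that fluctuations are located by injury month. Keep the look-back and, for a change at injury month m, extend the search for interviews and documents forward to about m+3 in the subacute series and about m+2 in the acute series.

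In Topic A, draw the policy timeline with the matching offset: for each event, mark the injury months whose 0-6 or 6-12 week window spans the event date. This keeps the planned denominators by injury month and needs no new data.

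The cost is a few sentences, a change to how the overlay is drawn, and a few more documents to read per fluctuation.
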